## **Outcome Measures**

### **Primary Outcome Measures:**

1. Number of examined participants with diabetes per retina specialist working hour
  - a. Number of examined participants with diabetes per retina specialist working hour. Numerator is the number of examined participants (including persons evaluated by autonomous AI on Intervention Days who are determined not to need to see the retina specialist). The denominator is retina specialist working time in hours.
2. Number of (all) patients per retina specialist working hour
  - a. Number of examined patients (all types) per retina specialist working hour. Numerator is the number of examined participants (including persons evaluated by autonomous AI on Intervention Days who are determined not to need to see the retina specialist). The denominator is retina specialist working time in hours.

### **Secondary Outcome Measures:**

1. Change in complexity score
  - a. Change from baseline in mean complexity score of participants seen per hour per retina specialist. The complexity score is determined by external masked graders using a standard system adapted from Wilkinson et al. International Clinical Diabetic Retinopathy (DR) and Diabetic Macular Edema (DME) Severity Scales. The complexity score for an eye will be the sum of points with higher score as increased complexity (0=No or Mild Non-Proliferative DR (NPDR), 1 = Moderate NPDR or Severe NPDR, 3 = Proliferative DR (PDR), 2 = DME), and for a person it will be the sum of both eyes.
2. Satisfaction with autonomous AI assessed by questionnaire.

- a. Retina specialist, technician and participant satisfaction with autonomous AI assessed by questionnaire using a 5 point Likert scale (1 = Very Satisfied 2 = Satisfied, 3 = Dissatisfied, 4 = Very Dissatisfied and 5 = N/A).

**Outline of main analysis:** Raw and adjusted (for above physician and patient predictors of productivity) intra-group difference in change in the number of patients with diabetic retinopathy passing through the clinic per hour per physician, cases of DR treated per week, and complexity score for each ophthalmologist.

### **Inclusion Criteria:**

Retina specialists regularly seeing patients with DR

- Routinely examines  $\geq$  20 patients with diabetes without known diabetic retinopathy or diabetic macular edema per week
- Routinely provides laser treatment or intravitreal injections to  $\geq$  3 DR patients/month

### AI Participants

- Diagnosed with type 1 or 2 diabetes
- $\geq 22$  years
- Presenting visual acuity  $\geq 6/18$  best corrected visual acuity in the better-seeing eye

### **Exclusion Criteria:**

Retina specialists:

- Currently using an AI system integrated into their clinical care and/or inability to provide informed consent.

### AI Participants:

- Inability to provide informed consent or understand the study; persistent vision loss, blurred vision or floaters; previously diagnosed with diabetic retinopathy or diabetic macular edema; history of laser treatment of the retina or injections into either eye, or any history of retinal surgery; contraindicated for imaging by fundus imaging systems

## B-PRODUCTIVE Statistical Analysis Plan

### 1. Background and Design

The purpose of the study is to assess the impact of using autonomous artificial intelligence (AI) (IDx-DR, Digital Diagnostics, USA) for identification of diabetic retinopathy (DR) and diabetic macular edema on productivity of retina specialists in Bangladesh. The **Bangladesh PRODUCTIVity in Eyecare (B-PRODUCTIVE)** Trial is a cluster-randomized (by clinic day) controlled trial. The trial will take place at a single clinic, Deep Eye Care Foundation (DECF), in Bangladesh collaborating with the on-going Orbis World Diabetes Federation DR project.

### 2. Outcome Measures

#### 2.1. Main Study Outcome:

The number of examined patients with diabetes per retina specialist working hour between AI and non-AI days.

- Numerator: number of examined patients
  - Sum of the number of patients diagnosed with diabetes mellitus (type 1 or type 2) examined for DR per day
  - Patients included have not been previously diagnosed with DR
  - Includes all patients evaluated by autonomous AI on AI days, even if they are not seen by the retina specialist
- Denominator: retina specialist working time (hours)
  - Sum of retina specialist time spent on all diabetes patients examined per day
  - Does not include patient time spent during autonomous AI evaluation
  - Excluding treatment or surgical time
  - Including retina specialist time spent on ordering & reviewing diagnostic studies and scheduling treatment/surgery

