## Final Protocol

### Bangladesh PRODUCTIVity in Eyecare (B-PRODUCTIVE) Trial

**Sponsor:** Orbis

**Collaborators:** Digital Diagnostics Inc. and Deep Eye Care Foundation (DECF)

**Study Aim:** To assess the impact of using autonomous artificial intelligence (AI) for identification of diabetic retinopathy (DR) and diabetic macular edema on productivity of retina specialists in Bangladesh.

**Hypothesis:** Autonomous AI increases retina specialist productivity

**Main Study Question:** Will retina specialists complete a greater number of diabetic eye exams per working hour (including persons reviewed by AI whom the retina specialist does not need to see personally) when they use autonomous AI in a randomized clinical trial?

**Design:** Cluster-randomized (by clinic day) controlled trial.

**Randomization:** By clinic day. Each morning the clinic manager will be notified if it is an Intervention (AI) or Control (non-AI) day.

**Interventions:** All patients in both groups go through the eligibility checklist. If approved, they will be evaluated by autonomous AI. This is done to decrease potential bias (neither patients nor physicians know the group assignment of participants) and concealment (so that neither patients nor doctors can arrange visits on a known "Intervention Day").

**Intervention Group:** On randomly selected "Intervention" clinic days, if patients screen positive or have insufficient image quality, they continue to the retina specialist. If not eligible for autonomous AI, they proceed straight to the retina specialist without autonomous AI evaluation. If patients receive a negative result, they do not see the retina specialist, and are referred for a visit at the regular eye clinic (not the retina clinic) in 3 months.

**Control Group:** On randomly-selected "Control Days," all patients see the retina specialist, irrespective of the results of autonomous AI evaluation.

**Masking:** The retina doctors are masked both patient group assignment (that is, whether autonomous AI was used for pre-screening or not on the particular clinic day)

and also masked to the results of the AI on Intervention days. Patients are also masked to group assignment and autonomous AI results.

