## 5. Randomization and Masking

The Bangladesh **PRODUCTIV**ity in **Eyecare** (B-PRODUCTIVE) Trial is a cluster-randomized (by clinic day) controlled trial. The study will assess the change in number of examined patients with diabetes per retina specialist working hour for three fully-qualified ophthalmologists regularly seeing patients with DR. All eligible patients (aged  $\geq 22$ , known diabetes, no previous DR diagnosis, consented) receive autonomous AI for DR detection. This is done for purposes of masking (neither patients nor physicians know the group assignment of eligible patients) and concealment. On randomly selected “Intervention” clinic days, if eligible patients receive a positive DR diagnosis or have insufficient image quality, they continue to the ophthalmologist. If eligible patients receive a negative DR diagnosis, they do not see the retina specialist, and are referred for a visit at the regular eye clinic (not the retina clinic) in 3 months. On randomly selected “Control Days,” all patients see the ophthalmologist, irrespective of the results of the autonomous AI report. The retina doctors are masked both to patient group assignment (that is, whether autonomous AI was used or not on the particular clinic day) and also masked to the results of the autonomous AI on Intervention days. Patients are also masked to group assignment and autonomous AI results.

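### SAP 2.1 credits every AI-evaluated patient on AI days, while the protocol credits without a specialist visit only those the AI clears; if uncleared patients leave unseen, the rule favours AI

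*Combined protocol and SAP*

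**What the plan says.** The primary outcome is a daily rate: diabetes patients examined, divided by retina specialist hours.

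- **SAP 2.1, general numerator rule:** "Sum of the number of patients diagnosed with diabetes mellitus (type 1 or type 2) examined for DR per day".
- **SAP 2.1, added rule for AI days:** "Includes all patients evaluated by autonomous AI on AI days, even if they are not seen by the retina specialist". It is not restricted by AI result.
- **SAP 2.1, denominator:** "Sum of retina specialist time spent on all diabetes patients examined per day". A patient who leaves before the specialist adds nothing to it.
- **Protocol, Primary Outcome Measures:** the count is widened only by "including persons evaluated by autonomous AI on Intervention Days who are determined not to need to see the retina specialist". The Main Study Question agrees: "including persons reviewed by AI whom the retina specialist does not need to see personally".
- **Care pathway on AI days (protocol, Intervention Group):** "if patients screen positive or have insufficient image quality, they continue to the retina specialist". SAP section 5 says the same.
- **Care pathway on control days (SAP section 5):** "all patients see the ophthalmologist, irrespective of the results of the autonomous AI report".

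The AI is run on eligible patients on both kinds of day, for masking and concealment. Neither document says how to count someone who has had the AI evaluation, is due to see the specialist, and leaves first.

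**The concern.** Crediting AI-negative patients without a specialist visit is the effect the trial sets out to measure, and nobody should object to it. The difficulty lies with the other AI-evaluated patients, those with a positive or insufficient-quality result. They are meant to go on to the specialist. If one of them leaves, the literal SAP rule still records an examination on an AI day, at no cost in specialist hours. On a control day the same patient, with the same AI evaluation and the same early departure, appears to count for nothing.

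Randomization does not balance this out, because the counting rule itself depends on arm. Equal leaving rates on the two kinds of day would still raise only the AI-day rate. Two analysts, one following the SAP and one the protocol, could also obtain different primary results from the same data.

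**Working it through.** **The plan's own figures.** SAP section 4 gives means of 1.34 and 1.68 per hour (difference 0.34), average cluster size 8, coefficient of variation 0.45, intra-cluster correlation 0.15, alpha 5%, power 80% and N = 924. No standard deviation is stated. Assuming a two-sided test and variance equal to the mean:

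- n per arm before clustering = (1.960 + 0.842)² × (1.34 + 1.68)/0.34² ≈ 205
- design effect = 1 + [(1 + 0.45²) × 8 − 1] × 0.15 = 2.293
- total = 942, which is 1.9% above 924

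The stated size is thus reproduced closely, although another assumption (equal clusters, variance 1.68 in both arms) gives 936, also close. The counting rule is not an input, so 924 is unaffected. What matters here is the yardstick: a control rate of 1.34 and a planned difference of 0.34.

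**Set-up.** Take N AI-evaluated patients on a day. Let p be the AI-negative share and l the share of the remaining patients who leave before the specialist. Assume each patient seen takes a constant t = 1/1.34 hours. Neither p nor l is given in the documents.

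On an AI day:

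- patients seen = N(1 − p)(1 − l), and hours = N(1 − p)(1 − l)t
- SAP numerator = N
- protocol numerator = Np + N(1 − p)(1 − l)
- difference in numerators = N(1 − p)l
- difference in rates = N(1 − p)l / [N(1 − p)(1 − l)t] = **1.34 × l/(1 − l)**

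The share p cancels, so the excess is the same however many patients the AI clears. On a control day, if only patients the specialist examined count, a leaver drops out of both numerator and hours, and the rate stays at 1.34.

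**Results.** Two values of p are shown: p = 0 (the AI clears nobody) and p = 0.34/1.68 = 20.2% (the share that turns 1.34 into 1.68 when nobody leaves).

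| l (assumed) | Excess per hour | Share of 0.34 | p = 0: SAP / protocol | p = 20.2%: SAP / protocol |
|---|---|---|---|---|
| 0% | 0 | 0% | 1.340 / 1.340 | 1.680 / 1.680 |
| 2% | 0.027 | 8% | 1.367 / 1.340 | 1.714 / 1.687 |
| 5% | 0.071 | 21% | 1.411 / 1.340 | 1.768 / 1.698 |
| 10% | 0.149 | 44% | 1.489 / 1.340 | 1.867 / 1.718 |

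Two points follow from the table and the model:

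- The protocol wording is not wholly immune. At p = 20.2% its rate rises from 1.680 to 1.698 when l = 5%, because leavers reduce specialist hours while AI-negative patients still count.
- The model treats every counted patient as AI-evaluated. Patients not eligible for AI go straight to the specialist and add hours under either rule, so for a given l they would make the excess smaller than shown.

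**The case against.** The strongest reply is that the SAP bullet is shorthand. In both documents the only AI-evaluated patients who are meant not to see the specialist on an AI day are the AI-negative ones. Read alongside the protocol and SAP section 5, the bullet may have been meant for them alone. If every patient follows the pathway, the two numerators are identical and the bias is exactly zero. That is correct as far as it goes, but it requires every positive or ungradable patient to reach the specialist. It also argues for the edit, since the SAP would then say what the protocol says.

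Three further objections stand and limit the point:

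- **The control-day rule is inferred.** SAP 2.1 says only that patients are examined for DR. That AI evaluation alone does not count on control days follows from the credit being confined to AI days. The inference is reasonable, but it is not a stated rule.
- **No leaving rate is given.** Patients are masked to their AI result, so a positive result gives them no particular reason to go. Every value of l above is an assumption.
- **Flow reporting is partly covered.** SAP 6.1 already plans a cluster CONSORT diagram of participant flow.

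A reader might also infer that a deferred patient would be counted twice, once on the AI day and again when seen. The documents do not support this as a finding. They describe no rescheduling of such patients, and SAP 2.1 excludes those previously diagnosed with DR, which might remove an AI-positive patient who returns.

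**Conclusion.** The SAP and the protocol define the primary numerator differently. Followed literally, the SAP rule depends on arm for uncleared patients who leave unseen, and the error can only favour AI. Its size is 1.34 × l/(1 − l) per hour: about 0.03 to 0.15 for l between 2% and 10%, or 8% to 44% of the planned difference, and nothing at all if nobody leaves. This rests on constant specialist time per patient seen, an assumed l, and the inferred control-day rule.

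A reader might go further and conclude that walk-outs do produce a false AI gain in this trial, or that they could account for the whole planned effect. Solving 1.34 × l/(1 − l) = 0.34 gives l = 0.34/1.68 = 20.2%, but that rate is found by working backwards and nothing in the documents suggests it. The supported conclusion is conditional. This should be fixed before analysis; it is not a must-fix defect.

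**What to change.** Replace the AI-day bullet in SAP 2.1 with a rule that matches the protocol, for example:

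> On AI days, count AI-evaluated patients with a negative result plus patients the retina specialist examined that day. All other patients count only when the specialist examines them, as on control days.

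This also puts the control-day rule in writing. SAP 2.2.1 (all clinic patients) gives no numerator rule of its own and should refer to the same one.

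In the CONSORT diagram already planned in SAP 6.1, report by arm the number of AI-evaluated patients who left before the specialist. If there are any, add a sensitivity analysis for the residual described above. One option is to count leavers as examined in both arms at the mean specialist time per patient seen, which under the model here returns 1.68 and 1.34.

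The cost is small: one sentence, no new visit, no change to the care pathway and no change to the sample size. AI results must be known in order to route patients, but SAP 3.1 does not name them as an analysis data item, so they should be added to the list. The AI-day rate may come out slightly lower than under the present wording.

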#### 2.2 Secondary outcomes:

- 2.2.1 Number of examined patients (all clinic patients, not only patients with diabetes) per retina specialist working hour between AI and non-AI days
- 2.2.2 Number of patients with diabetic retinopathy per day scheduled for any treatment including injections, implants, laser or surgery.
- 2.2.3 Retina specialist and AI-eligible patient satisfaction with autonomous AI.
- 2.2.4 Mean complexity score of patients seen per hour per retina specialist.

### 3. Data

#### 3.1. Data collection methods

- 3.1.1. Ophthalmologist clinic records as audited by study personnel.

- 3.1.2. Masked documentation of physician time spent with patients.
- 3.1.3. Complexity score for each patient will be calculated by a masked UK NHS grader using the International Grading system, which is adapted from Wilkinson et al. International Clinical Diabetic Retinopathy and Diabetic Macular Edema Severity Scales.
- 3.1.4. AI-eligible patient and Specialist questionnaires.

### 3.2. Data Completion

- Questionnaires will be completed by specialist participants at the end of the trial.
- AI-eligible patient demographic data will be completed prior to the AI exam, and applicable satisfaction surveys will be completed following the AI exam.
- Specialist hours will be tracked daily for clinic time and number of clinic exams completed by each specialist will be tracked daily (all patients examined and patients with diabetes examined)

## 4. Sample Size Calculations

The null hypothesis is that diabetic patients without known DR seen by retina specialist per doctor hour for regular clinic days and AI days are the same. We are estimating the sample size needed to reject this null hypothesis. In calculating the sample size we used 80% power (the probability of rejecting a false null hypothesis). The sample size estimate is 924 patient participants.

Inputs for the sample size estimate calculations are:

- 80% power; power is the probability of rejecting a false null hypothesis.
- Alpha of 5%; probability of rejecting a true null hypothesis.
- Average cluster size of 8 and cluster size coefficient of variation of 0.45 (based on March data).
- Mean number of diabetic patients without known DR seen per doctor hour is 1.34 (based on Quarter 1 data). Hospital records that were used to calculate the sample size show that there are approximately 366 diabetic patients seen at the hospital per month. The retina clinic examines approximately 237 patients with diabetes per month.
- We changed some factors, but decided on one estimate.

Mean of Group 1	Mean of Group 2	Mean Difference	Intra-cluster correlation coefficient	Sample Size estimate
-----------------	-----------------	-----------------	---------------------------------------	----------------------

1.34	1.68	0.34	0.15	924
------	------	------	------	-----

## 5. Randomization and Masking

The Bangladesh **PRODUCTIV**ity in **Eyecare** (B-PRODUCTIVE) Trial is a cluster-randomized (by clinic day) controlled trial. The study will assess the change in number of examined patients with diabetes per retina specialist working hour for three fully-qualified ophthalmologists regularly seeing patients with DR. All eligible patients (aged  $\geq 22$ , known diabetes, no previous DR diagnosis, consented) receive autonomous AI for DR detection. This is done for purposes of masking (neither patients nor physicians know the group assignment of eligible patients) and concealment. On randomly selected “Intervention” clinic days, if eligible patients receive a positive DR diagnosis or have insufficient image quality, they continue to the ophthalmologist. If eligible patients receive a negative DR diagnosis, they do not see the retina specialist, and are referred for a visit at the regular eye clinic (not the retina clinic) in 3 months. On randomly selected “Control Days,” all patients see the ophthalmologist, irrespective of the results of the autonomous AI report. The retina doctors are masked both to patient group assignment (that is, whether autonomous AI was used or not on the particular clinic day) and also masked to the results of the autonomous AI on Intervention days. Patients are also masked to group assignment and autonomous AI results.

## 6. Analysis

Raw and adjusted (for above physician and patient predictors of productivity) group differences in the number of patients with diabetic retinopathy passing through the clinic per hour per physician will be calculated for AI and non-AI days. The two clinic day patient groups will be compared with Chi-square testing for categorical variables. Age as a continuous variable was summarized with mean and standard deviation and the two groups will be compared with the student t-test.

Study outcomes of encounters per retina specialist hour and confidence intervals will be calculated for each clinic day for all patients, as well as specifically for diabetic patients and retina specialty patients. Rates will be compared across AI and non-AI clinic days with student t-testing. Associations between the main outcome, diabetic patients examined per hour, and potential predictors will be assessed utilizing linear regression modeling with generalized estimating equations that include clustering effect of day. Residuals will be assessed to confirm that a linear model fits the rate outcome. A multivariable model will include sex, gender and variables that have  $p\text{-value} < 0.10$  in the univariate analysis.

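### SAP 6 and the protocol outline set the adjusted difference on patients with diabetic retinopathy, not on the primary outcome, and leave the adjusted model under-specified

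*Combined protocol and SAP*

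**What the plan says.** **Outcome.** The protocol's first primary outcome is "Number of examined participants with diabetes per retina specialist working hour". SAP 2.1 gives the main outcome as "The number of examined patients with diabetes per retina specialist working hour between AI and non-AI days" and adds two rules for the numerator: "Patients included have not been previously diagnosed with DR" and "Includes all patients evaluated by autonomous AI on AI days, even if they are not seen by the retina specialist". SAP 4 uses the same population: "The null hypothesis is that diabetic patients without known DR seen by retina specialist per doctor hour" is equal on regular and AI days.

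**Analysis.** SAP 6 opens by promising raw and adjusted "group differences in the number of patients with diabetic retinopathy passing through the clinic per hour per physician", to be calculated for AI and non-AI days. The protocol's outline of main analysis, at the end of Secondary Outcome Measures, promises a raw and adjusted "intra-group difference in change in the number of patients with diabetic retinopathy passing through the clinic per hour per physician". Both say that the adjustment is for physician and patient predictors given above.

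The second paragraph of SAP 6 returns to patients with diabetes. Rates for all, diabetic and retina specialty patients are compared between day types by t-test. A linear GEE model with clustering by day then relates the diabetic-patient rate to potential predictors. Its multivariable version takes sex, gender and any variable with a univariate p-value below 0.10.

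**The concern.** The sentence that promises an adjusted AI versus non-AI difference names a population that is not the primary one. If it is followed as written, the adjusted result describes different patients from the raw primary result beside it. The patients left out would include the AI-negative ones, whom AI spares a specialist visit and whom SAP 2.1 deliberately counts.

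The model that does carry the right outcome cannot be reproduced from the text. It does not name the treatment contrast as a term, it refers to a list that is not there, and it lets the outcome data choose the covariates. Two competent analysts could report different adjusted differences and both claim to have followed the plan.

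**Working it through.** **1. Population and contrast, place by place**

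| Place | Patients counted | Contrast |
|---|---|---|
| Protocol, first primary outcome | Diabetes, including those cleared by AI on intervention days | Not worded in the item |
| SAP 2.1 | Diabetes, no earlier DR diagnosis, including AI-evaluated patients not seen | AI v non-AI days |
| SAP 4 | Diabetes without known DR | AI v regular days |
| SAP 6, t-test | All, diabetic, and retina specialty patients | AI v non-AI days |
| SAP 6, GEE | Diabetes | None named |
| SAP 6, first sentence | DR | AI v non-AI days |
| Protocol outline | DR | Within-group change |

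The last two rows stand apart on population, and the last also on contrast.

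**2. Effect of the literal wording on the numerator.** Start from the SAP 2.1 numerator. Counting only patients with DR removes everyone in whom none is found, including the AI-negative patients on AI days. Unless restricted further, it also admits patients with known DR, whom SAP 2.1 leaves out. Specialist hours fall too when AI-negative patients are not seen, so a DR rate could still differ between day types. The documents give neither the share of patients with DR nor the time per patient, so the direction and size of the discrepancy cannot be worked out.

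**3. Sample size.** Inputs from SAP 4: means 1.34 and 1.68 per doctor hour, ICC 0.15, cluster size 8, coefficient of variation 0.45, 80% power, alpha 5%, total 924. No SD, sidedness or allocation ratio is given, so 924 cannot be reproduced from these inputs alone. Assuming two-sided alpha and 1:1 allocation:

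- Difference: 1.68 − 1.34 = 0.34.
- Design effect: 1 + ((1 + 0.45²) × 8 − 1) × 0.15 = 2.293.
- Effective size per arm: 462 / 2.293 = 201.5.
- Implied SD: √[201.5 × 0.34² / (2 × (1.960 + 0.842)²)] = 1.22.
- With an assumed Poisson variance, (1.34 + 1.68) / 2 = 1.51 and SD = 1.229. The total is then 942, which is 18 (1.9%) above 924.

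The stated figure is therefore consistent with a calculation on the diabetic-patient rate. Correcting the DR label changes none of its inputs.

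**4. Can the adjusted model be built from the text?**

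- Outcome: stated in the GEE sentence, and correct.
- Day type: not named. Day appears only as the clustering unit.
- Predictors given above: none are listed before either sentence. SAP 6.2 comes later and lists baseline characteristics without calling them covariates.
- Forced terms: sex and gender. SAP 6.2 has sex but no separate gender variable. One of the two may be a slip for another variable, but the documents do not say.
- Other terms: whatever passes p<0.10, from no stated candidate list.
- Available data: SAP 3.2 and 6.2 describe patient demographics only for AI-eligible patients. The main numerator is wider, because AI eligibility also depends on age, acuity, symptoms and consent. By contrast, specialist hours are recorded daily and "number of clinic exams completed by each specialist will be tracked daily", so who worked on each clinic day is known for every day.

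**The case against.** The strongest reply is that the DR wording is a leftover. Most of the text agrees on the diabetic-patient rate, SAP 6 compares that rate between day types by t-test, and the GEE sentence calls it the main outcome. This stands. A reader might infer that the primary analysis is set on the wrong population or that the trial is under-powered. The documents support neither: the unadjusted comparison has the right outcome, SAP 4 is computed for the right patients, and a power figure for a DR rate would need a DR share that is not given.

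A second reply is that day type is plainly meant to be in the model. A reader might infer the opposite, that day type must pass the p<0.10 screen and could drop out. The text resists that: SAP 6 says adjusted differences will be calculated for AI and non-AI days, which a model without day type cannot supply. No probability of omission is therefore claimed. What remains is that an implied term is not a specified one. Even with day type supplied, the covariate list is missing, and correcting the DR label does not fill it.

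A third point limits the remedy. In the protocol outline, the phrase about within-group change also governs the complexity score, which the protocol defines as a change from baseline and SAP 2.2.4 as a mean. Replacing the phrase throughout would create a new contradiction.

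**Conclusion.** The concern holds for the adjusted analysis and should be fixed before day types are compared. Two places name patients with DR where the primary outcome is patients with diabetes, the protocol outline also words the contrast as a within-group change, and the adjusted model lacks a named treatment term and a usable covariate list.

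The size is bounded by what is untouched: the t-test on the diabetic-patient rate, and 924. The conclusion rests on reading the sentences as written. The only numerical assumptions, two-sided alpha, equal allocation and Poisson variance, serve the consistency check on 924 and do not bear on the finding.

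**What to change.** 1. In SAP 6 and the protocol outline, replace the DR label with the SAP 2.1 main outcome. For that productivity outcome, state the contrast as AI days versus non-AI days. Reconcile the complexity-score wording separately between the protocol's secondary outcomes and SAP 2.2.4.
2. State that day type is a fixed term in the GEE model of diabetic patients examined per specialist hour, kept whatever its univariate p-value, and that its coefficient with 95% CI is the adjusted difference.
3. For this estimate, replace the unlisted predictors, sex and gender, and the p<0.10 screen with a short pre-specified list of covariates recorded for every unit analysed, for example which specialists worked that clinic day. Use patient age and sex only if they are recorded for the whole numerator.
4. Fit the model to the clinic-day rate, so that AI-evaluated patients whom no specialist saw need not be assigned to one. With one record per day, each cluster holds a single record and the GEE reduces to linear regression with robust standard errors. If the average cluster of 8 is patients per clinic day, 924 / 8 = 115.5, or about 116 records, which suits a short list.

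The cost is small: text edits, and a fixed covariate list in place of data-driven selection. The sample size does not change. The suggested specialist covariate is already recorded.

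### The chi-square tests and the age t-test in SAP section 6 ignore allocation by clinic day, so their p-values are too small if same-day patients are alike; the productivity analyses are unaffected

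*Combined protocol and SAP*

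**What the plan says.** The protocol describes the design as a "Cluster-randomized (by clinic day) controlled trial". SAP section 4 allows for this when it sets the sample size. It lists "Average cluster size of 8 and cluster size coefficient of variation of 0.45", and its table gives an ICC of 0.15 and a total of 924 patients.

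SAP section 6 covers two kinds of comparison:

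- **Patient characteristics.** "The two clinic day patient groups will be compared with Chi-square testing for categorical variables". For age, "the two groups will be compared with the student t-test". No allowance for day is stated. Section 6.2 lists the patient characteristics as age, sex and estimated monthly income.
- **Productivity.** Rates are calculated per clinic day and compared between AI and non-AI days by t-test. The regression models use GEE with clustering by day.

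SAP 2.2.3 lists as a secondary outcome "Retina specialist and AI-eligible patient satisfaction with autonomous AI". Section 6 names no method for it.

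**The concern.** Ordinary chi-square and t-tests assume that every patient is an independent observation. Here everyone attending on a given day falls in the same arm. Anything that makes same-day patients alike (referral patterns, weekday, weather, outreach activity) therefore adds variation between arms that these tests do not count. The standard error is then too small and the p-value too low.

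The plan recognises day clustering in its sample size and in its outcome models. These two sentences are the exception.

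Two things are at stake. A chance difference in age, sex or income between arms could be reported as a significant imbalance more often than 5% of the time. Also, the chi-square sentence is not limited to baseline variables. An analyst with no other instruction could apply it to the satisfaction responses, which are categorical, and report a difference between arms that reflects day-to-day variation.

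**Working it through.** **Inputs from SAP section 4.** Mean cluster size m = 8; coefficient of variation of cluster size CV = 0.45; planning ICC = 0.15 (for the productivity outcome); total 924 patients, or 924/8 = 115.5, about 116 clinic days; alpha 5%. Sidedness is not stated, so two-sided is assumed.

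**Input not in the documents.** The day ICC of age, sex, income or satisfaction. Values from 0 to 0.15 are tried.

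**The plan's own figure.** 924 cannot be reproduced from the stated inputs because no SD is given. Assume a Poisson SD of √1.51 = 1.229 (1.51 is the mean of 1.34 and 1.68), equal arms, two-sided 5% and 80% power. This gives 206 per arm before clustering. Multiplying by the design effect of 2.293 derived below gives a total of 942 to 946, depending on rounding, which is within 3% of 924. Other SDs with other design effects also come close, so this does not show which design effect was used. Both are carried forward.

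**Step 1: design effect.**
- Equal cluster sizes: DE = 1 + (m − 1) × ICC. At 0.15: 1 + 7 × 0.15 = 2.05.
- Variable cluster sizes: DE = 1 + [(1 + CV²) × m − 1] × ICC. At 0.15: 1 + (1.2025 × 8 − 1) × 0.15 = 1 + 8.62 × 0.15 = 2.293.

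**Step 2: true size of an unadjusted nominal 5% test.** Size = 2 × [1 − Φ(1.96/√DE)]. The true standard error exceeds the reported one by the factor √DE.

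| Day ICC | DE (equal / variable) | √DE | True size |
|---|---|---|---|
| 0 | 1.00 / 1.00 | 1.00 / 1.00 | 5.0% / 5.0% |
| 0.01 | 1.07 / 1.086 | 1.03 / 1.04 | 5.8% / 6.0% |
| 0.05 | 1.35 / 1.431 | 1.16 / 1.20 | 9.2% / 10.1% |
| 0.15 | 2.05 / 2.293 | 1.43 / 1.51 | 17.1% / 19.6% |

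At ICC 0.15 with variable sizes, 924 patients carry the information of 924/2.293 = 403 independent ones, and a reported p of 0.01 corresponds to about 0.09.

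**Step 3: check by simulation.** 116 days, 58 per arm, mean size 8, CV about 0.45, no true difference, 3,000 runs per ICC.

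| Day ICC | Patient-level t-test | Patient-level chi-square | t-test on day means / day proportions |
|---|---|---|---|
| 0 | 4.9% | 5.3% | 5.0% / 4.8% |
| 0.01 | 5.5% | 6.2% | 4.8% / 4.8% |
| 0.05 | 10.0% | 9.9% | 4.8% / 5.3% |
| 0.15 | 18.5% | 20.2% | 4.9% / 4.8% |

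The formula and the simulation agree. Taking the day as the unit restores the nominal size at every ICC tried. The figures apply to the t-test and to a chi-square on a two-category variable. They do not cover tables with more categories.

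**The case against.** The strongest reply is that these are baseline comparisons with no consequence. The two sentences sit together, section 6.2 lists only age, sex and income for patients, and no decision depends on the resulting p-values. The p < 0.10 screen for the multivariable model is most naturally read as using the day-clustered GEE models. Much of this stands, and it limits the importance of the point. It does not make the tests valid: if the plan reports p-values, they should respect the unit of randomisation.

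Three stronger readings are tempting, and the documents do not support them.

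- **That the main result is at risk.** A reader might infer that the plan's "Alpha of 5%; probability of rejecting a true null hypothesis" is exceeded for the primary comparison. That alpha belongs to the productivity hypothesis. Section 6 calculates those rates for each clinic day, which is the randomised unit, and clusters the regression models by day.
- **That the error is 17% to 20%.** This borrows the ICC of 0.15 planned for patients per doctor hour. Nothing in the documents says that age, sex, income or satisfaction cluster as strongly.
- **That the chi-square sentence governs satisfaction.** This is an inference from silence. No between-arm test of satisfaction is stated. AI-eligible patients on both kinds of day have the AI exam, are masked to group and complete the survey after that exam, so a single-group description is a natural reading. Specialists answer once, at the end of the trial, and have no arm to compare. What stands is that section 6 leaves the method open and the sentence is not confined to baseline variables.

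**Conclusion.** The point holds for the patient-level comparisons in section 6. As written, the chi-square tests and the age t-test are anti-conservative for any positive day ICC. The size is uncertain: no inflation at ICC 0, slight at 0.01, up to a doubling of the nominal error rate at 0.05, and three to four times nominal only at 0.15.

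This rests on a two-sided 5% level, on the cluster size and CV in section 4, and on assumed ICCs. That the productivity analyses are unaffected rests on the t-test using one rate per clinic day, as section 6 says. The same section also speaks of rates per physician. If several physician rates per day entered the t-test, the day would again have to be accounted for.

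For satisfaction the conclusion is conditional: the problem arises only if the arms are compared and an unadjusted test is used. This is a wording correction worth making, and it does not threaten the primary conclusion.

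**What to change.** Replace the two sentences in SAP section 6 with one of these:

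- describe age, sex and income by arm, without p-values; or
- compare them with a method that accounts for clinic day, either GEE (logistic or linear) with robust standard errors by day, or tests on day-level means and proportions.

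Add one sentence stating that any between-arm comparison of patient satisfaction (2.2.3) will also use a day-clustered method or, if none is intended, that satisfaction will be described only.

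No extra patients or procedures are needed. Each patient's clinic day should be recoverable from the allocation by day and the daily tracking in SAP 3.2, but the data manager should confirm that it is held in the patient-level file. The downside is wider intervals and larger p-values for these comparisons: standard errors rise by about 4% at ICC 0.01, 20% at 0.05 and 50% at 0.15.
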